TITLE: Pharmacokinetics and pharmacodynamics of the etonogestrel contraceptive implant when co-administered with efavirenz

NCT: NCT01980342

DATE: January 5th 2017

PI: [name], MPH

JHM IRB - eForm A – Protocol

1. Abstract

Women of reproductive age who are living with HIV have to navigate complex decisions regarding fertility, contraception, and managing their HIV diagnosis. One consideration for HIV-infected women who want or need to prevent pregnancy is whether the medications used to treat HIV could reduce the efficacy of a contraceptive method through drug-drug interactions. Efavirenz (EFV) is a non-nucleoside reverse transcriptase inhibitor (NNRTI) that is an important component of first-line antiretroviral therapy worldwide. However, in addition to having a side effect profile that leads some to discontinue therapy, Efv has been associated with failures of a highly effective hormonal contraceptive, the etonogestrel (ENG) implant. A recent multi-center trial suggests that a lower Efv dose retains efficacy against HIV while reducing the incidence of side effects. We propose a pilot study to evaluate the effect of reduced dose Efv on the pharmacokinetics of the ENG implant. We will recruit 18 HIV-negative healthy women who have had the implant in place for 6 to 30 months. They will be asked to take a two-week course of reduced dose efavirenz. During these two weeks and for four additional weeks, we will monitor semi-weekly ENG concentrations, and serum, ultrasound, and cervical mucus markers of ovulation. We will also assess Efv concentration at baseline, the end of the two-week treatment course, and at the end of the study. We will derive pharmacokinetic parameters and compare concentrations across time points. Results will help determine whether the ENG implant can be used safely by HIV-positive women taking Efv, and will help to inform the design of similar larger studies with different antiretroviral medications.

2. Objectives

The primary objective of this study is to determine whether etonogestrel (ENG) pharmacokinetics in users of the ENG contraceptive implant (Nexplanon®/Implanon®) are affected by concomitant administration of a reduced dose of oral efavirenz (EFV).

Secondary objectives are:

- To determine if co-administration of reduced-dose efavirenz with the ENG contraceptive implant results in pharmacodynamic changes that suggest increased risk of ovulation and consequently decreased contraceptive efficacy.

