This will be a prospective, single arm pilot pharmacokinetic (PK) study. We will recruit 18 healthy, HIV-negative women aged 18 to 40 years who are using Nexplanon®/Implanon® for contraception and who are willing to take a reduced dose of EFV for 2 weeks. We will limit enrollment to women who have had the ENG implant in place 12 to 24 months to avoid the initial burst release of ENG after implant placement, and to target the time frame of concern based on case studies of contraceptive failures among women on HAART. Performing the study in women without HIV infection will allow us to evaluate any interactions between ENG and EFV without having to contend with the effects of other drugs that make up typical HAART regimens. A two-week course of EFV will be sufficient for EFV to reach steady-state concentration while minimizing exposure in these healthy volunteers. By using the reduced dose of EFV (400 mg daily instead of the standard 600 mg daily dose)

Over 6 weeks from study entry, we will perform twice-weekly (see visit schedule) quantitative assessments of serum ENG as well as serum hormone concentration analysis, pelvic ultrasound for markers of ovulation, and cervical mucus testing, as described below. Given the slow apparent clearance of ENG and based on previous PK studies, we estimate that sparse sampling will be adequate to assess changes in ENG clearance during EFV administration. EFV will be administered for 14 days from the beginning of the study, after collection of baseline samples for ENG concentration determination. All study procedures will take place at the Johns Hopkins Bayview Medical Center's Clinical Research Unit (CRU). All blood tests will be performed locally except for ENG concentrations, which will be performed at Columbia University

Date: January 5th, 2017

Principal Investigator: [name], MPH

Application Number: NA_00087585

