Transvaginal ultrasound (TVUS) will be performed using high-resolution machines (Sonosite Edge, SonoSite, Inc., Bothell, WA) in our clinic to monitor follicular development. Follicular diameter will be calculated by averaging the mean of the length and width in both the sagittal and transverse plane. Follicles measuring ≥ 10 mm will be considered dominant preovulatory follicles, and only follicles measuring ≥ 10 mm will be recorded[20]. Ovulation will be defined as the disappearance of a follicle ≥ 15 mm in diameter that was observed the visit before. We will collect cervical mucus using an endocervical aspirator, and evaluate the sample for consistency, ferning, Spinnbarkeit, and cellularity. Each variable will be scored on a 0 to 3 point scale according to WHO guidelines. A total score of 9 to 12 will indicate mucus conditions favorable to sperm penetration[21].

Recruitment: Subjects will be recruited from the general gynecology office in JHOC and practices affiliated with JHBMC. We will recruit patients known to be using Nexplanon®/Implanon®. Written notices advertising the study will be placed in the gynecology offices as well as in other affiliated primary care offices. We will also place advertising notices throughout Johns Hopkins institutions including the School of Nursing and the School of Public Health.

b. Study duration and number of study visits required of research participants.

Date: January 5th, 2017

Principal Investigator: [name], MPH

Application Number: NA_00087585

We anticipate that the study will take 12 months to complete. Participants will be enrolled for a total of 6 weeks (2 weeks taking EFV, and 4 weeks additional follow-up), during which time they will complete 14 visits including a screening visit. After enrollment, visits will occur twice weekly.

c. Blinding, including justification for blinding or not blinding the trial, if applicable.

Not applicable in this pilot pharmacokinetic study

d. Justification of why participants will not receive routine care or will have current therapy stopped.

Not applicable.

e. Justification for inclusion of a placebo or non-treatment group.

Not applicable.

f. Definition of treatment failure or participant removal criteria.

Treatment failure is not applicable to this study as efavirenz is being given to healthy volunteers and not part of an HIV treatment regimen. A participant will be removed from the study under the following circumstances:

- She misses more than three study visits

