- Nervous system symptoms: dizziness, insomnia, impaired concentration, somnolence, abnormal dreaming, euphoria, confusion, agitation, amnesia, hallucinations, stupor, abnormal thinking, depersonalization. Mild symptoms occurred in 33.3% of patients taking EFV compared to 15.6% of patients in control groups; moderate symptoms occurred in 17.4% of patients taking EFV compared to 7.7% of controls; and severe symptoms occurred in 2% of patients taking EFV compared to 1.3% of controls.
- Rash: 26% of patients taking EFV developed a rash compared to 17% of patients in control groups. A grade 4 rash (erythema multiforme, Stevens-Johnson syndrome, toxic epidermal necrolysis, necrosis requiring surgery, exfoliative dermatitis) was seen in 0.1% of patients treated with EFV and no patients in control groups. Rashes usually occur during the first two weeks of treatment, and are mild-to-moderate maculopapular skin eruptions. The rash typically resolves within one month in patients who continue EFV.
- Hepatotoxicity: it is recommended that liver enzymes be evaluated before and during treatment with EFV, as EFV can cause elevated liver enzymes even in patients without underlying hepatic disease.
- Convulsions: Convulsions have been noted in patients treated with EFV, typically in the setting of a known seizure disorder.
- Lipid elevations: EFV can lead to increased concentrations of total cholesterol and triglycerides. Some HIV-uninfected volunteers who received EFV were noted to have 10-20% increases in total cholesterol from baseline.

Date: January 5th, 2017

Principal Investigator: [name], MPH

Application Number: NA_00087585

- **Fat redistribution:** Body fat may redistribute or accumulate in certain regions of the body, including central obesity, dorsocervical fat enlargement (buffalo hump), peripheral wasting, facial wasting, breast enlargement, and “cushingoid appearance.” This phenomenon has been noted among patients taking antiretroviral therapy in general, and while it has not been specifically linked to EFV, it is a potential adverse reaction to this drug.
- c. Justification and safety information if non-FDA approved drugs without an IND will be administered.

Not applicable

7. Study Statistics

- a. Primary outcome variable.

Primary Outcome: Serum concentrations of ENG before and after two weeks of reduced-dose EFV

- b. Secondary outcome variables.

Secondary Outcomes:

- Serum concentrations of EFV at the start and end of the study period

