- Serum hormonal markers of ovulation (P, E₂, LH, FSH)
- Presence of dominant follicle(s) on transvaginal ultrasound during and after EFV dosing
- Change in cervical mucus quality suggesting ovulation during and after EFV dosing

- c. Statistical plan including sample size justification and interim data analysis.

Sample size: We hypothesize that during co-administration of the ENG implant and reduced-dose EFV, we will detect a decrease in serum ENG concentrations, but that overall contraceptive effect will be maintained. We do not anticipate that any subjects will have a drop in ENG concentration below the threshold needed for ovulation suppression (90 pg/mL)[8]. Using a two-sided Wilcoxon test, a sample size of 15 will have 80% power (with an alpha of 0.05) to detect a 20% difference in ENG concentration between women taking EFV and historical controls. We plan to enroll 18 women to account for a potential 20% drop-out rate.

Data Analysis: We will calculate area under the curve (AUC) and maximum and minimum concentrations of each drug (C_{max} and C_{min}), as noted above. For hormone markers (LH, FSH, E₂, P) we will evaluate change over time as well as whether pertinent threshold levels are reached that could indicate that ovulation has occurred. All serum tests will be evaluated through the Johns Hopkins Division of Clinical Pharmacology, with the exception of etonogestrel concentrations as this assay is not widely available. Serum samples will be frozen and shipped to the Irving Institute for Clinical and Translational Research at Columbia University Medical Center in New York City, which will perform the etonogestrel assay.

Interpretation: If the pharmacokinetic parameters for etonogestrel that are seen in this interaction study are consistent with those published in the literature (less than 30% difference), we will conclude that there is no significant interaction between ENG and reduced-dose EFV. This would support the assertion that Nexplanon®/Implanon® is a safe and effective option for HIV-infected women taking reduced-dose EFV who desire long-acting reversible contraception. However, if two or more women out of a sample of 15 breach the threshold concentration needed for ovulation suppression, it will indicate a statistically and clinically significant decrease in ENG concentration and potential for decreased contraceptive efficacy.

Date: January 5th, 2017

Principal Investigator: [name], MPH

Application Number: NA_00087585

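### Enrolling 18 women does not cover a 20% drop-out from a required 15: it covers at most 3 losses (16.7%)

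*Combined protocol and SAP*

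**What the plan says.** The sample-size paragraph in Section 7c of the combined protocol and SAP bases the study's power on 15 women: "a sample size of 15 will have 80% power (with an alpha of 0.05) to detect a 20% difference in ENG concentration". It then sets the enrolment: "We plan to enroll 18 women to account for a potential 20% drop-out rate".

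The enrolment figure is consistent across the document. Section 4a has "We will recruit 18 healthy, HIV-negative women aged 18 to 40 years", and the abstract also gives 18. The figure of 15 appears again in the interpretation paragraph of Section 7c, where the rule on falling below the ovulation-suppression threshold counts women out of 15.

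Section 7a defines the primary outcome as "Serum concentrations of ENG before and after two weeks of reduced-dose EFV". Section 4f lists the grounds for removing a participant, among them "She misses more than three study visits", and Section 7d adds more. No section says that a woman who leaves will be replaced. The plan gives no formula for the step from 15 to 18.

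**The concern.** A drop-out rate is normally a proportion of the women enrolled, because only they can drop out. On that meaning, the required number, the enrolment and the allowance in Section 7c cannot all be right: losing 20% of 18 leaves fewer than 15.

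This paragraph is the plan's only justification of its enrolment. A reader would take from it that the study can lose a fifth of its participants and still have the number on which both the power statement and the threshold rule rest. The margin is in fact smaller than that.

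**Working it through.** **Inputs, all from Section 7c:** required number 15; planned enrolment 18; drop-out allowance 20%.

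**Reproducing the plan's figure.** Adding 20% to the required number gives 15 × 1.2 = 18, which matches exactly. The three extra women are 3 / 15 = 20% of those retained. This is the likely source of the 18, although the plan does not say so.

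**Checking what 18 covers.** With drop-out as a share of those enrolled:

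- Expected to finish at 20% drop-out: 18 × (1 − 0.20) = 14.4, which is 0.6 below 15.
- Three losses: 18 − 3 = 15 remain; 3 / 18 = 16.7%.
- Four losses: 18 − 4 = 14 remain; 4 / 18 = 22.2%.

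**Enrolment needed for a 20% allowance.** 15 / (1 − 0.20) = 18.75, rounded up to 19. Check: 19 × 0.8 = 15.2. The shortfall is 19 − 18 = 1 woman.

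**Effect on power, for scale only.** The 80% at 15 women cannot be reproduced, because the plan gives no standard deviation, no number of historical controls and no form of the Wilcoxon test. Taking the 80% as an assumption and using a normal approximation (1.96 + 0.84 = 2.80):

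- One-sample reading: power = Φ(2.80 × √(n/15) − 1.96).
- Two-sample reading with m controls: power = Φ(2.80 × √[(1/15 + 1/m) / (1/n + 1/m)] − 1.96).

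| Reading | n = 14.4 | n = 14 |
|---|---|---|
| One-sample | 78.4% | 77.2% |
| Two-sample, m = 10 | 79.3% | 78.9% |
| Two-sample, m = 15 | 79.2% | 78.6% |
| Two-sample, m = 100 | 78.6% | 77.6% |

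The results use unrounded constants; the rounded ones shown shift some entries by 0.1 point. The values of m are assumed, to show the range. A one-sample t-test scaled to 80% at 15 gives 78.1% at 14.4 and 76.8% at 14. The loss is therefore about 1 to 2 points at 14.4 women and about 1 to 3 points at 14.

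**Chance of keeping 15, for illustration.** If each woman independently had a 20% chance of dropping out (an assumption), the probability of retaining at least 15 would be about 50% with 18 enrolled and about 67% with 19.

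**The case against.** The strongest reply is that the numbers agree if the 20% is read as an uplift on the required 15, since 15 × 1.2 is exactly 18. The plan also never says in so many words that 15 women will remain. The first part explains the error but does not remove it: an uplift on the number retained is not a drop-out rate, and 18 still tolerates only 16.7%. The second part is literally true. That 15 are meant to remain is an inference, but a firm one, because both the power statement and the threshold rule are set at 15.

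The second reply is that almost nothing follows from it. This stands in large part. The study is a single-arm pilot, the gap is one woman, and the 20% is itself only a possibility. Drop-out over six weeks is also not the same as loss of primary data. Etonogestrel is sampled on Day 1 and Day 14 (Table 1), so a woman who leaves in Weeks 3 to 6 may already have contributed to the primary outcome. These points limit the consequence without reconciling the figures, and the plan has no definition of an evaluable participant that would turn a 20% drop-out into a 16.7% loss.

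A third reply is that restating the allowance fits the assumption to the enrolment. That is fair if the investigators truly expect to lose 20%. In that case 19 is the number that matches their expectation.

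**Conclusion.** The concern holds, as a minor arithmetic error. With 18 enrolled the plan can lose three women (16.7%) and keep 15; at the stated 20% the expected number finishing is 14.4. The shortfall is one enrolled woman.

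This conclusion assumes only that a drop-out rate is a share of those enrolled, that 15 is the number to be retained, and that drop-outs are not replaced. It does not depend on whether the 80% power is correct. The power losses of 1 to 3 points do depend on that figure and indicate size only. The error does not threaten the study's conclusions.

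**What to change.** Replace the enrolment sentence in Section 7c with: *18 women allow for up to 3 drop-outs (16.7%) while retaining 15.* This is correct as arithmetic and agrees with the 18 in the abstract and Section 4a. Do not insert a recalculated power figure, because the documents lack the inputs to support one.

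The cost is one sentence and a stated allowance that falls from 20% to 16.7%. Enrolment, design and analysis do not change. If the investigators want to keep the 20%, the consistent alternative is to enrol 19 and amend the 18 wherever it appears, but a gap this small does not require it.

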Data collection: After successful screening, women will be asked to take 14 days of EFV in a once-nightly 400 mg regimen. We will collect blood samples for baseline ENG concentration on the day participants begin taking EFV, before the first dose (Day 1, times 0 hour, 1 hour, and 2 hours). The first dose of EFV will be taken in the evening of Day 1, and the next blood sample for ENG concentration will be drawn twelve to twenty hours after the first dose of EFV. (For example, if a participant takes her first dose of EFV at 10 PM on Day 1, she will be asked to return to the CRU between 10 AM and 6 PM on Day 2.) We will then obtain subsequent samples every 3 to 4 days (+/- 1 day) for the remainder of the two week EFV course and for 4 additional weeks (through Week 6 of study participation). This is a total of 14 outpatient visits, including screening. All serum samples will be analyzed for concentrations of ENG, which will be used to derive the ENG area under the concentration-time curve (AUC), the maximum and minimum observed serum drug concentration (C_{max}, C_{min}), and the apparent average serum concentration at steady-state (C_{ss,avg}) using WinNonlin®. EFV concentrations will be determined from plasma samples obtained at 2 timepoints during EFV administration, and measured using a validated LC/MS/MS assay in the Clinical Pharmacology Analytical Laboratory of the Johns Hopkins Hospital.

Table 1: Participant Visit Schedule and Timing of Study Assessments

Visit	Screening	Study Entry			Week 1		Week 2		Week 3		Week 4		Week 5		Week 6	
		1			2	7	11	14	18	21	25	28	32	35	39	42
Serum Tests		0 hr	1 hr	2 hr												
ENG		X	X	X	X	X	X	X	X	X	X	X	X	X	X	X
EFV					X			X								
FSH		X			X	X	X	X	X	X	X	X	X	X	X	X
LH		X			X	X	X	X	X	X	X	X	X	X	X	X
Estradiol		X			X	X	X	X	X	X	X	X	X	X	X	X
Progesterone		X			X	X	X	X	X	X	X	X	X	X	X	X
Safety Labs	X															X
UPT	X															X
HIV	X															X
TVUS	X				X	X	X	X	X	X	X	X	X	X	X	X
CM	X				X	X	X	X	X	X	X	X	X	X	X	X

Date: January 5th, 2017

Principal Investigator: [name], MPH

Application Number: NA_00087585

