Secondary endpoints will be serum markers of ovulation (estradiol [E₂], progesterone [P], follicle stimulating hormone [FSH], and luteinizing hormone [LH]), as well as evidence of ovulation on cervical mucus exam and transvaginal ultrasound (presence and subsequent disappearance of a dominant follicle >15 mm diameter)[19]. Blood for hormone assays will be drawn at the Bayview CRU at the same time as samples for ENG and EFV. During these visits participants will also undergo a pelvic exam for cervical mucus assessment, and a pelvic ultrasound to look for ovarian follicular activity. Monitoring throughout the study will allow us to compare ovarian activity across time points through both ultrasound visualization and ovarian hormone testing (E₂ and P). Changes in cervical mucus quality secondary to the progestin activity of ENG provide secondary contraceptive effects that may be maintained even if ovulation occurs. Continued monitoring for several weeks after cessation of EFV will allow us to follow subjects for the equivalent of a normal menstrual cycle, to ascertain whether either contraceptive effect (ovulation suppression or cervical mucus quality) was altered. Urine pregnancy tests may be repeated throughout the duration of the study as needed.

Ultrasounds and venipuncture for LH, FSH, E₂ and P levels will occur in the CRU. A total of 20 mL of venous blood will be collected for each outpatient visit. FSH, LH, E₂, and P assays will be performed by the CRU at JHU. FSH and LH will be measured using the automated immunoradiometric assay (IRMA) system. Assay sensitivity of LH assays is 0.07 mIU/ml; assay sensitivity of FSH assays is 0.2 mIU/ml. P will be measured using an automated immulite chemiluminescent assay system. Assay sensitivity of the P assay is 0.05 ng/ml. E₂ will be measured via an ultra-sensitive competitive binding radioimmunoassay with sensitivity of 2.2 pg/ml. The EFV assay will be performed through the Johns Hopkins Hospital Clinical Pharmacology Analytical Lab, and will be measured via LC-MS/MS assay with a lower limit of quantification of 0.5 ng/ml.

An assay for ENG is not commercially available, but the Irving Institute for Clinical and Translational Research at the Columbia University Medical Center in New York has developed a validated assay. ENG concentrations will be measured by LC-MS/MS, and the assay has a lower limit of quantification of 50 pg/ml.

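### Section 7c promises AUC, Cmax and Cmin for efavirenz as well as etonogestrel, but the two efavirenz samples and the methods stated cannot give valid steady-state values

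*Combined protocol and SAP*

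**What the plan says.** - Section 7c (Data Analysis): "We will calculate area under the curve (AUC) and maximum and minimum concentrations of each drug", with a reference back to the earlier text for how.
- Section 2: a secondary objective on EFV pharmacokinetic parameters, judged against levels expected from historical controls. No historical source is named.
- Section 4a (Data collection), the text 7c refers back to: ENG concentrations are the ones "which will be used to derive the ENG area under the concentration-time curve (AUC", together with "the maximum and minimum observed serum drug concentration" and an average steady-state concentration, using WinNonlin. For EFV the same paragraph says only "EFV concentrations will be determined from plasma samples obtained at 2 timepoints during EFV administration".
- Table 1: EFV is marked on Day 2 and Day 14 and nowhere else.
- Section 4a, timing: on Day 2 "the next blood sample for ENG concentration will be drawn twelve to twenty hours after the first dose of EFV". After that, "We will then obtain subsequent samples every 3 to 4 days (+/- 1 day) for the remainder of the two week EFV course". EFV and ENG share visits: "Blood for hormone assays will be drawn at the Bayview CRU at the same time as samples for ENG and EFV".
- Section 1 (Abstract): EFV is to be assessed at three times, namely baseline, the end of the two-week course and the end of the study.
- Section 7b: the EFV outcome is its serum concentration at the start and end of the study period.

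**The concern.** A stated analysis should be one that the sampling schedule can support. Section 7c commits to exposure parameters for two drugs, but only ENG has a concentration profile. An analyst who followed 7c literally for EFV would have either no usable AUC, or a maximum and minimum taken over two values that do not describe the same exposure. Those two numbers could easily be read as peak and trough.

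The historical comparison in section 2 has the same weakness. A single EFV concentration can be set against published values only if its time after the last dose is known. The plan fixes that time for Day 2 but not for Day 14, and it names no comparison source. The reference value could therefore be picked after the results are known.

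At stake is the EFV secondary objective. No test or decision rule rests on it.

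**Working it through.** **Sample counts (Table 1).** ENG: 3 on Day 1 (0, 1 and 2 h) + 12 later visits (Days 2, 7, 11, 14, 18, 21, 25, 28, 32, 35, 39, 42) = 15. EFV: Day 2 + Day 14 = 2, which reproduces the two timepoints in the section 4a text.

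**Where the EFV samples fall.** Dosing is once nightly for 14 days from the evening of Day 1, giving 14 intervals of nominally 24 h. A daytime draw on Day d follows d − 1 doses.
- Day 2: after 2 − 1 = 1 dose, 12 to 20 h post-dose (a window of 20 − 12 = 8 h).
- Day 14: after 14 − 1 = 13 doses. If the one-day tolerance applies to the Table 1 day, the visit falls on Day 13 to 15, after 12 to 14 doses.

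The two samples are 12 × 24 = 288 h apart at equal clock times. With the protocol's example visit hours of 10 AM to 6 PM, the gap is 280 to 296 h. Two of the 14 intervals are sampled, once each.

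**What each parameter would be for EFV.**
- *AUC.* At steady state there is one value, so no area over a dosing interval can be calculated without a model. In the first interval a zero start is implied if the woman has had no earlier EFV. Joining it to the Day 2 value gives a crude partial single-dose area, not a steady-state AUC.
- *Cmax and Cmin.* As observed values they exist, but they are just the larger and smaller of a first-dose value and a value after about 13 doses.
- *Model-based values.* These would need a population model or a limited-sampling equation. None is named, and the sparse-sampling justification in section 4a concerns ENG clearance.

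**Illustration under assumed kinetics.** The documents give no EFV half-life or absorption rate. Assume one compartment, constant clearance, half-life 20 to 76 h and absorption rate ka 0.15 to 1.2 per h. With elimination rate ke = ln 2 / half-life, and concentrations in units of dose over volume,

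C(t) = Σ [ka/(ka − ke)] × [exp(−ke·u) − exp(−ka·u)], with u = t − 24i, summed over the doses i already taken.

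Once absorption is complete, the ratio of Day 14 to Day 2 at the same post-dose time is [1 − exp(−13·24·ke)] / [1 − exp(−24·ke)].
- Half-life 20 h: exp(−24·ke) = 2^(−1.2) = 0.435, and the numerator is close to 1. Ratio = 1/0.565 = 1.77.
- Half-life 76 h: (1 − 0.0581)/(1 − 0.8034) = 0.9419/0.1966 = 4.79.

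Over the whole grid, with draws at 12 or 20 h, slow absorption raises the upper end:

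| Quantity | Range |
|---|---|
| Day 14 / Day 2 concentration | 1.77 to 5.64 |
| True interval Cmax / Day 14 sample | 1.01 to 1.78 |
| True interval Cmin / Day 14 sample | 0.66 to 0.95 |
| Trapezoid through both samples / true 24 h AUC | 6.8 to 10.0 |

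The observed maximum and minimum would thus mostly reflect accumulation between Day 2 and Day 14, not the swing within a dosing interval. A trapezoid through both points spans 288 h and is not a dosing-interval AUC.

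**Sampling days compared.**

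| Source | EFV times |
|---|---|
| Section 4a text | two, both during dosing |
| Table 1 | Day 2, Day 14 |
| Abstract | baseline, end of course, end of study |
| Section 7b | start and end of study period |

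The Abstract's end-of-study time has no counterpart: Day 42 is 42 − 14 = 28 days after the last EFV sample. Its baseline has none either if it means pre-dose, as it does for ENG ("We will collect blood samples for baseline ENG concentration on the day participants begin taking EFV, before the first dose"). Table 1 has no EFV mark on Day 1.

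**The case against.** The best defence is that the operative text is already right. Section 4a derives parameters for ENG and promises only concentrations for EFV, section 7b lists an EFV concentration as the outcome, and 7c defers to 4a. On that view the fault is two loose phrases, one in 7c and one in section 2. This stands in part, since it shows where the wording should end up. But section 2 is a stated objective, and 7c explicitly extends the parameters to both drugs, so the plan commits to something its schedule does not support.

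Several stronger readings are tempting, and the documents do not support them:
- *That no EFV AUC could be obtained by any method.* A model-based estimate is possible with an outside model. The fault is that none is named.
- *That no interval has two points.* The first interval has the implied zero start noted above.
- *That only one of the Abstract's three EFV times is in Table 1.* This depends on taking baseline strictly as pre-dose. If it loosely means the first EFV sample, two of three match. Only the end-of-study time is missing on either reading.
- *That section 7b contradicts Table 1.* Its start and end may mean those of dosing, so it is ambiguous.

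It is also fair that this is an untested, descriptive objective in a single-arm pilot, which limits the harm from a comparison value chosen late. And the documents identify no source of historical EFV levels, so close matching on post-dose time cannot be assumed feasible. The low-dose EFV trial cited in section 8a is used there for adverse reactions.

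**Conclusion.** The concern holds for EFV under the methods the plan states. With one sample after the first dose and one after about 13 doses, no valid steady-state AUC, Cmax or Cmin can be obtained, and the two-value maximum and minimum mix single-dose with multiple-dose exposure. Day 14 is the only EFV sample that can stand for steady state, relying on section 4a's statement that two weeks is long enough to reach it. Bedtime dosing (section 8b) and a daytime visit suggest a mid-interval draw on Day 14, but no window is stated and no recording of last-dose time is described.

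The counts (15 against 2 samples, 2 of 14 intervals) come straight from Table 1 and the dosing schedule. The dose count at Day 14 assumes a daytime visit and no missed doses. The model ranges rest on assumed kinetics, and the conclusion does not depend on them.

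A reader might infer that the trial's main result is compromised. It is not: the primary outcome and the interpretation rules in 7c use ENG only.

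**What to change.** 1. In section 7c, restrict AUC, Cmax and Cmin to ENG.
2. Reword the EFV objective in section 2 and the EFV outcome in 7b to the EFV concentration at Day 14, with the times of the last dose and of the draw recorded.
3. Report the Day 2 value separately as a single-dose concentration.
4. Make any comparison with historical values descriptive. Name the source before the EFV results are seen, and take post-dose time into account as far as that source allows.
5. Bring the Abstract and 7b into line with the EFV days in Table 1.

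This needs protocol wording and the recording of two times per EFV sample, with no extra visits, samples or assays. Finding a suitable historical source is work that the documents do not show to be done. The downside is a narrower secondary objective: one timed concentration in place of pharmacokinetic parameters. If the parameters themselves are wanted, the alternatives are more samples within one dosing interval or a prespecified model, and both cost more.
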